**Comparative Effectiveness of Particulate Versus
Nonparticulate Corticosteroid Injections for the Treatment
of Musculoskeletal Conditions**

Study Protocol and Statistical Analysis Plan

NCT04278833

April 7, 2020

1) Name of study:

Comparative Effectiveness of Particulate versus Nonparticulate Steroid Injections for Treating Musculoskeletal Conditions

2) PI and other key investigators or key study personnel

PI: [name]

Investigator: [name]

Research coordinator: [name], CCRC

3) Specific source of institutional funding (account number): None**4) List of sources from whom you are seeking funds (or have sought funding) for this project**

AMSSM funding

Stanford internal funding

PM&R foundation

Charity from donors

5) Specific aims and basic hypothesis including an explicit primary hypothesis or goal**Specific Aims:**

- a. To determine if particulate or non-particulate corticosteroid injections are more effective at treating pain from musculoskeletal pathologies of the intra-articular hip, glenohumeral joint, biceps tendon, and subacromial bursa at 2 weeks, 3 months, or 6 months.
- b. To determine if there is a significantly different side effect profile between particulate and non-particulate corticosteroids when used for intra-articular hip, glenohumeral joint, biceps tendon, or subacromial bursa injections.

Hypothesis: There will be no significant difference in pain reduction, number of injections received, conversion to surgery, or side effect profile at 2 weeks, 3 months, or 6 months between particulate and non-particulate corticosteroids in the treatment of musculoskeletal pathologies of the intra-articular hip, glenohumeral joint, biceps tendon, or subacromial bursa.

6) General background

Corticosteroid injections are commonly used for the treatment of painful musculoskeletal pathologies including hip and glenohumeral joint osteoarthritis, adhesive capsulitis, biceps tendinopathy, and impingement syndrome/subacromial bursitis (Lambert et al, 2007; Lee et al, 1997; Yoon et al, 2013; Hong et al, 2011), yet there is no consensus on whether particulate or non-particulate steroids are superior. Particulate steroids include betamethasone, triamcinolone, and methylprednisolone, while non-particulate steroids include dexamethasone (Derby et al, 2008).

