After consenting, basic demographic data, average numeric pain score (NRS) over the past week, and information on other medical interventions tried for their pain (including medication use, physical therapy, chiropractic care, and massage) will be collected. The participant will then be randomized to receive either a particulate (triamcinolone or betamethasone) or non-particulate (dexamethasone) corticosteroid, both of which are within current standards of care. Ultrasound or fluoroscopic guided injection will then be completed using sterile technique as per current clinic practice.

After the injection, patients will follow up in clinic or over the phone at 2 weeks, 3 months, and 6 months and will be asked their average NRS over the past week, functional questionnaires appropriate to pertinent body parts (WOMAC, ASES, QDASH), other treatments they have tried in the interim, and for any side effects they have experienced. In addition to obtaining outcome measures, the treating physicians may order repeat injections, medications, or refer the subject to surgery, at their discretion based upon the patient's pain and functional limitations. Up to a total of three injections to the same musculoskeletal structure are allowed during the 6 month study period. Any injection into a separate space (i.e. glenohumeral joint followed by subdeltoid bursa) will be considered different structures, and follow up for the new anatomical site will begin at the time of that injection. Data collection and follow up on the previous anatomical injection site will continue on the same timeline. Data on number and timing of repeat injections, surgeries, side effects, and medications will be recorded as part of the study.

Data analysis

Patients receiving injections to the intra-articular hip, glenohumeral joint, peri-tendinous biceps, and subdeltoid bursa will be analyzed separately. Depending on normality and cell counts, baseline measures between the particulate and non-particulate injection groups will be compared using two-sample t-tests or Mann-Whitney U-tests for continuous variables and chi-squared tests or Fisher's exact tests for categorical variables.

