Within each joint/structure, a mixed-effects model will be used to compare differences in pain (NRS), function (WOMAC, ASES, QDASH), and the number of subsequent injections. These models will include adjustments for repeated measures and potential covariates as determined by the previous univariate tests. A power analysis determined that a sample size of 50 (25/group) will provide at least 80% power to detect 10% differences in pain and 25% differences in function between patients receiving particulate and non-particulate corticosteroids in the subdeltoid bursa and intra-articular hip, while a sample size of 36 (18/group) achieves the same power for patients receiving treatment in the glenohumeral joint, and a sample size of 62 (31/group) achieves this power in the biceps brachii group.

The time until a repeat injection was administered will be analyzed using a Cox proportional hazards survival model and chi-squared tests will be used to analyze repeat injections, repeat surgeries, and side effects between groups. All statistical analyses will be completed using a two-sided level of significance of 0.05.

Inclusion Criteria

- Age greater than or equal to 18
- Ability to provide informed consent
- Capable of complying with the outcome instruments used
- Capable of attending all planned follow up visits
- Patient is deemed appropriate for intra-articular hip, glenohumeral, peri-tendinous biceps, or subdeltoid bursa corticosteroid injection by their treating physician for the treatment of a painful musculoskeletal condition

-Average pain of greater than or equal to 4/10 over the last 7 days

Exclusion Criteria

- Unclear diagnosis
- Pregnancy
- Incarcerated patients
- Prior corticosteroid injection into the anatomical structure within the past 3 months
- Prior prosthetic surgery on the joint
- Any condition that increases injection risk such as bleeding tendencies, uncontrolled diabetes, current active infection, or infection requiring antibiotics within the last 7 days
- Chronic opioid use to control pain
- Workers compensation and litigation.
- BMI > 40

Data safety monitoring

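### Glenohumeral diagnosis is not listed as recorded and is not prespecified in the model, which costs precision and leaves chance imbalance uncorrected at 18 per arm

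*Combined protocol and SAP*

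**What the plan says.** Section 6 (General background) lists the indications for these injections as "hip and glenohumeral joint osteoarthritis, adhesive capsulitis, biceps tendinopathy, and impingement syndrome/subacromial bursitis". Two of them, osteoarthritis and adhesive capsulitis, belong to the glenohumeral joint. The inclusion criteria in section 8 set no diagnosis for that joint; any painful condition that the treating physician judges suitable for the injection qualifies. One exclusion is "Unclear diagnosis", so a diagnosis has to be established for each patient at screening.

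The baseline data named under Design are "basic demographic data, average numeric pain score (NRS) over the past week, and information on other medical interventions tried for their pain". Diagnosis is not among them. Randomisation is to one of two steroid types, with no method, blocking or stratification described.

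Under Data analysis, "Patients receiving injections to the intra-articular hip, glenohumeral joint, peri-tendinous biceps, and subdeltoid bursa will be analyzed separately". The mixed model takes its covariates from the preceding univariate baseline comparisons between arms; none is prespecified. On size, "a sample size of 36 (18/group) achieves the same power for patients receiving treatment in the glenohumeral joint", that power being the one under which the samples "will provide at least 80% power to detect 10% differences in pain and 25% differences in function". On the test level, "All statistical analyses will be completed using a two-sided level of significance of 0.05".

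**The concern.** Osteoarthritis and adhesive capsulitis need not follow the same course over 6 months. If they do not, diagnosis is a prognostic factor inside a cohort of 36. Leaving it out of the model puts the difference between diagnoses into the residual variance, and any chance imbalance in diagnosis stays in the estimated arm difference at 3 and 6 months.

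The plan's only route for diagnosis into the model is a baseline significance test. That route first requires diagnosis to be recorded in analysable form, which the plan does not say. It then relies on a test with little power at 18 per arm.

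Lost power matters here because the hypothesis in section 5 is that no significant difference will be found, a result that extra noise makes easier to reach.

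**Working it through.** **Inputs from the plan.** 18 per arm, at least 80% power, a 10% pain difference, two-sided 0.05. No SD, case mix or information on natural course is given.

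**Assumptions.** Diagnosis mix 50:50 or 30:70; course difference (gap) between diagnoses of 1, 2 or 3 NRS points; within-diagnosis SD of 1, 2 or 2.5; 10% read as 1 NRS point.

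**1. The plan's own figure.** Without an SD, 18 per arm cannot be reproduced, only solved backwards. The standardised difference is (1.960 + 0.842) × √(2/18) = 0.934 (normal), or 0.961 with the t distribution. For 1 point, the implied SD is 1/0.934 = 1.07 or 1/0.961 = 1.04. If 10% is instead relative to a baseline of 4 to 8, the implied SD is 0.4/0.934 = 0.43 to 0.8/0.934 = 0.86. SD 1 is therefore close to what the plan implies on the 1-point reading; 2 and 2.5 show what happens if pain scores vary more.

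**2. Chance imbalance.** With the count of one diagnosis in each arm as an independent Binomial(18, p):
- p = 0.5: P(difference ≥ 4) = 0.243; P(≥ 6) = 0.065.
- p = 0.3: P(≥ 4) = 0.201; P(≥ 6) = 0.044.

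**3. Shift in the arm difference.** Shift = gap × imbalance/18. For an imbalance of 4 this is 0.22, 0.44 and 0.67 points for gaps of 1, 2 and 3.

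**4. Would the baseline test bring diagnosis in?**
- 11 v 7 of 18: chi-squared (uncorrected) p = 0.18, Fisher p = 0.32.
- 12 v 6 of 18: chi-squared p = 0.046, Fisher p = 0.094.

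So at a 50:50 mix the chi-squared test needs a difference of about 6. Of the draws with a difference of 4 or more, roughly 0.065/0.243 = 27% would be flagged, and fewer with Fisher.

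**5. Type I error.** A simulation of 200,000 trials, comparing arms at a single visit as a simplification of the mixed model, gives overall unadjusted error of 0.049 to 0.051 in every scenario. Conditional on an imbalance of 4 or more with a 2-point gap, the error is 0.15 at SD 1 and 0.09 at SD 2. Well-balanced draws offset this: with an imbalance of at most 1 (SD 2, 2-point gap) the error is 0.03. With diagnosis in the model it is about 0.05 even when the imbalance is 6 or more.

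**6. Power for a 1-point effect.** Without the term, total SD = √(SD² + 0.25 × gap²) at a 50:50 mix; with it, the gap drops out. Noncentrality = √(18/2)/SD = 3/SD, on 34 degrees of freedom. Example: SD 1 and gap 2 give √(1 + 1) = 1.414, noncentrality 3/1.414 = 2.12, power 54%.

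| Within-diagnosis SD | With term | Without, gap 1 | Without, gap 2 | Without, gap 3 |
|---|---|---|---|---|
| 1.0 | 83% | 74% | 54% | 37% |
| 2.0 | 31% | 29% | 26% | 21% |
| 2.5 | 21% | 21% | 19% | 17% |

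The simulation, which charges the covariate for its degree of freedom and for imbalance, gives 82% rather than 83% at SD 1 and 30% rather than 31% at SD 2. At a 30:70 mix the factor 0.25 becomes 0.3 × 0.7 = 0.21, so the losses are somewhat smaller.

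**The case against.** A reader might infer that differing natural courses could pass as a steroid effect, that is, confound the comparison. The documents do not support this. Treatment is randomised, so an omitted prognostic factor neither biases the comparison systematically nor raises the overall 5% error, as step 5 shows. Chance imbalance is already reflected in the standard error. The conditional error in an unlucky draw is real, but the argument is one of precision. This part of the objection stands in full.

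A reader might also infer that diagnosis is not collected. That rests on silence in a one-sentence summary of baseline data, not on a case report form, and the exclusion of unclear diagnoses points the other way. What can be said is that diagnosis is not listed as recorded or used.

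The size is also open to challenge. At SD 2.5 the standard error of the arm difference is 2.5 × √(2/18) = 0.83, larger than any of the shifts in step 3, and the term gains at most about 4 percentage points of power. At that SD the cohort has little power for 1 point either way. The mix, the gap and the SD are all assumed. This stands, and it limits the severity.

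Finally, the aim is framed by site, so the trial need not answer a question about each disease. That is fair, and separate conclusions by disease are not required. It does not count against adjustment: a site-level comparison is also estimated more precisely when a strong prognostic factor is in the model. Selecting covariates by baseline tests is a weakness in all four cohorts; the glenohumeral joint is where the background names two distinct diseases and the cohort is smallest.

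**Conclusion.** The point holds as a matter of precision and prespecification. The plan allows a mixed-diagnosis glenohumeral cohort of 36, does not list diagnosis as recorded, and leaves its use to a test that would miss an 11 v 7 split.

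The benefit of a diagnosis term depends on quantities the plan does not give. It is substantial if the within-diagnosis SD is near the 1.04 to 1.07 points implied by the sample size and the courses differ by 2 points or more. It is slight if the SD is 2 or above and the gap is 1 point, and it vanishes if the courses are alike or nearly all patients share one diagnosis. The validity of the randomised test is not in question. This is a cheap improvement of minor to moderate severity.

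**What to change.** Add one REDCap field, completed before randomisation, for the diagnosis being treated in the glenohumeral joint: osteoarthritis, adhesive capsulitis or other. The third level is needed because eligibility is not limited to the two named diseases.

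Under Data analysis, state that the glenohumeral mixed model will include diagnosis and diagnosis-by-visit whatever the baseline comparisons show, and say in advance how a sparse third category will be handled.

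Stratifying the glenohumeral randomisation list by diagnosis is optional; the prespecified term already gives most of the benefit.

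The cost is one data field and a few degrees of freedom in a cohort of 36. With three categories and three follow-up visits, that is 2 for diagnosis and 2 × 2 = 4 for the interaction. If diagnosis turns out not to be prognostic, the loss is small: with a single diagnosis term, about 1 percentage point of power in the simulation.

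### Covariates enter the mixed models only if they differ between arms at baseline, and the role of baseline NRS is left unstated

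*Combined protocol and SAP*

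**What the plan says.** Section 8, Design, collects "basic demographic data, average numeric pain score (NRS) over the past week, and information on other medical interventions tried for their pain" after consent. The next step is randomisation: "The participant will then be randomized to receive either a particulate". A pre-randomisation pain score therefore exists for each participant at first entry.

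Section 8, Data analysis, first sets out the baseline comparison: "Depending on normality and cell counts, baseline measures between the particulate and non-particulate injection groups will be compared using two-sample t-tests", with Mann-Whitney, chi-squared and Fisher's exact tests as the alternatives. It then says that, within each structure, "a mixed-effects model will be used to compare differences in pain (NRS), function (WOMAC, ASES, QDASH), and the number of subsequent injections", and adds: "These models will include adjustments for repeated measures and potential covariates as determined by the previous univariate tests". The section closes with "All statistical analyses will be completed using a two-sided level of significance of 0.05".

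The documents contain no covariate list, no separate threshold for covariate selection, and no screening of covariates against outcome. Baseline NRS is not named as a covariate, a time-zero response or part of a change score. The hypothesis in section 5 is worded as "There will be no significant difference in pain reduction, number of injections received, conversion to surgery, or side effect profile", which is compatible with a change score but does not specify one.

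**The concern.** After randomisation, a between-arm baseline test asks only whether chance has produced a difference. The answer says nothing about how well the variable predicts follow-up pain, which is what decides whether adjustment is worthwhile. Under the rule a strong predictor that happens to be balanced is left out, and a useless one that happens to be imbalanced is put in. Because the four structures are analysed separately, their models could differ for no reason but chance.

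What is at stake is precision in groups of 18 to 31, and a clear statement of what the main pain model is. The same sentence also governs the function models and the model for number of subsequent injections.

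**Working it through.** **Inputs from the plan.** Two-sided 0.05; 25 per group (bursa, hip), 18 (glenohumeral), 31 (biceps); at least 80% power for a 10% difference in pain.

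**Inputs that are assumptions.** The correlation ρ between baseline and follow-up NRS (0.1, 0.3, 0.5, 0.7); selection at 0.05, the only level the plan gives; normal outcomes.

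**The plan's own figure.** The sample sizes cannot be reproduced, because no SD is given. For 80% power the noncentral t needs a standardised difference d of 0.961, 0.809 and 0.723 at 18, 25 and 31 per group. If 10% means 1 point on a 0–10 scale, the implied SDs are 1/d = 1.04, 1.24 and 1.38. The comparisons below use d, so they do not depend on that reading.

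**Step 1: how often baseline NRS enters.** Entry needs a chance difference of at least t(0.975, 2n−2)·√(2/n) SD. This is 0.68, 0.57 and 0.51 SD at 18, 25 and 31 per group. By construction it happens about 5% of the time. With simulated integer scores from 4 to 10 (20,000 trials), the t-test let it in 4.9%, 5.4% and 5.0% of the time and Mann-Whitney 4.5%, 5.0% and 4.9%.

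**Step 2: precision, free of any power assumption.** The variance of the adjusted difference relative to the unadjusted one is (1−ρ²)(1+1/(2n−4)). At n = 25 the second factor is 1+1/46 = 1.0217. A change score has relative variance 2(1−ρ).

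| ρ | Adjusted / unadjusted variance | Equivalent unadjusted n per group (25/ratio) | Change score / unadjusted |
|---|---|---|---|
| 0.1 | 0.99 × 1.0217 = 1.01 | 24.7 | 1.8 |
| 0.3 | 0.91 × 1.0217 = 0.93 | 26.9 | 1.4 |
| 0.5 | 0.75 × 1.0217 = 0.77 | 32.6 | 1.0 |
| 0.7 | 0.51 × 1.0217 = 0.52 | 48.0 | 0.6 |

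Adjustment breaks even where ρ² = 1/(2n−3), that is ρ = 0.17, 0.15 and 0.13 at 18, 25 and 31 per group.

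**Step 3: power at a single visit**, n = 25, effect set for 80% unadjusted power, 200,000 simulated trials per setting. The rule is: adjust if the baseline t-test gives p < 0.05, otherwise use the unadjusted t-test.

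| ρ | Rule | Always adjust | Gain over rule (points) | Change score |
|---|---|---|---|---|
| 0.1 | 79.8% | 79.5% | −0.3 | 55.1% |
| 0.3 | 80.1% | 82.7% | 2.6 | 65.9% |
| 0.5 | 80.9% | 89.2% | 8.3 | 80.1% |
| 0.7 | 82.0% | 97.3% | 15.3 | 95.2% |

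Results at 18 and 31 per group are nearly the same. If unadjusted power is really 90%, the gains are about 0, 2, 5 and 8 points; at 95%, about 0, 1, 3 and 4.

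**Step 4: mean of three visits**, n = 25, with assumed baseline correlations ρ, 0.8ρ and 0.6ρ, and follow-up correlations of 0.7 between adjacent visits and 0.5 between first and last. The rule gives 80/80/81/82% and always adjusting 79/82/88/95%, a gain of about nil, 2, 7 and 13 points.

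**Step 5: type I error**, n = 25. Always adjusting holds 5.0%. The rule gives about 4.9–5.0% at ρ = 0.1 and 4.8%, 4.3–4.4% and 3.6–3.7% at 0.3, 0.5 and 0.7, so it is slightly conservative overall. In null trials whose baseline p-value lies between 0.05 and 0.20, however, the rule leaves the imbalance uncorrected and rejects about 6%, 9% and 12% of the time at ρ = 0.3, 0.5 and 0.7. The adjusted analysis stays near 5% in those trials.

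**The case against.** The strongest reply is that the harm may be nil. A mixed model for repeated measures may already take baseline NRS as a response with a common mean across arms, and that uses the information about as well as a covariate does. The 5% figure concerns entry as a covariate only. This stands, but the plan does not say that this model is meant.

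Second, no document gives ρ, and the entry rule "Average pain of greater than or equal to 4/10 over the last 7 days" restricts the baseline range and so tends to lower it. The relevant gain may then be 0 to 3 points. The plan also claims at least 80% power, and a higher starting power shrinks the gain, as step 3 shows. Both points stand. They limit the size of the loss but give no reason to keep the rule: at ρ = 0.1 fixed adjustment costs at most about 0.6 of a point at any of the three group sizes.

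Third, the change-score figures do not measure the selection rule. They come from a possible reading of the hypothesis, and their gaps are largest where the rule costs nothing. That is fair. They show only why the role of baseline NRS should be stated, and they are not counted as a cost of the rule.

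Fourth, only NRS was simulated. The case for dropping the rule in the other models rests on the reasoning about randomisation, not on these figures.

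**Conclusion.** The concern holds. The plan states a selection rule that is unrelated to prognostic value, and it leaves the use of baseline NRS open. The cost is efficiency and clarity, not validity: overall type I error is not inflated. Against the rule, fixed adjustment gains from nothing at ρ = 0.1 to about 15 points of power at ρ = 0.7, for a single visit with 25 per group and 80% unadjusted power. The gain is smaller if true power is higher or the baseline range is narrow, and about nil if baseline NRS is already modelled as a response with a common mean. These figures rest on an assumed ρ, selection at 0.05 and normal outcomes. The change is worth making because the score is already collected and the downside is negligible.

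**What to change.** Replace the covariate sentence in section 8, Data analysis, with wording such as:

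> The models will account for repeated measures within participant. Each NRS model takes the 2-week, 3-month and 6-month scores as responses and includes baseline NRS, with its interaction with visit, as a fixed covariate whatever the result of any baseline test. A constrained longitudinal model with baseline as a response and a common baseline mean is an acceptable alternative. Where a pre-injection score of a function instrument is collected, the model for that instrument includes it in the same way. No covariate in any model, including that for number of subsequent injections, is selected by between-group baseline tests, which are descriptive only.

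Two definitions should go with it. First, state which score counts as baseline when a participant later enters for a second structure, since a score taken then would follow the first randomised treatment. Second, state which questionnaires are completed before the injection: Design names the function instruments only at follow-up, while the Procedure Plan marks questionnaires as not applicable at Baseline and as a study item at Injection.

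For first entries the cost is wording only. A single baseline slope uses one degree of freedom per model, and separate slopes for the three visits use three. The function clause applies only where a score already exists, so it adds no data collection.

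### Side effects (aim b) get only chi-squared tests, apparently within structures of 18 to 31 per arm, with no risk difference, confidence interval or combined comparison, so a non-significant result cannot support the hypothesis of no difference

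*Combined protocol and SAP*

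**What the plan says.** Section 5 lists two specific aims. Aim b looks for any "significantly different side effect profile between particulate and non-particulate corticosteroids when used for intra-articular hip, glenohumeral joint, biceps tendon, or subacromial bursa injections". The hypothesis that follows is one of absence: "There will be no significant difference in pain reduction, number of injections received, conversion to surgery, or side effect profile".

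The only method for side effects is in section 8, Data analysis: "chi-squared tests will be used to analyze repeat injections, repeat surgeries, and side effects between groups", at a two-sided 0.05 level. That sentence does not say whether the tests are run within structures. The mixed-model sentence does ("Within each joint/structure, a mixed-effects model will be used to compare differences in pain (NRS"), and the Data analysis part opens with a general statement: "Patients receiving injections to the intra-articular hip, glenohumeral joint, peri-tendinous biceps, and subdeltoid bursa will be analyzed separately".

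The sample sizes are 25 per group for bursa and hip, 18 for the glenohumeral joint and 31 for biceps. The stated basis is that they "will provide at least 80% power to detect 10% differences in pain and 25% differences in function". Side effects do not enter it.

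A participant may later be injected in another structure. In that case "follow up for the new anatomical site will begin at the time of that injection", and "Data collection and follow up on the previous anatomical injection site will continue on the same timeline". No rule says how such a participant is counted in the side-effect analysis.

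Under Data safety monitoring, minor side effects are actively asked about at 2 weeks, 3 months and 6 months. No expected rate is given.

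**The concern.** A chi-squared test returns a p-value, with no estimate of how far apart the arms are or could be. That matters most when the hypothesis is no difference, because in a small cohort a non-significant p-value is the likely result over a wide range of true differences. As the plan stands, four such results could be reported as confirming similar side-effect profiles when the data would still allow differences of 15 to 20 percentage points in either direction.

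The background section presents safety as part of the reason for comparing these drugs, and section 9 hopes the results will guide drug choice. A reader would therefore want to know which differences have been excluded. The planned output does not show this within a structure, and no analysis puts the four cohorts together.

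**Working it through.** **Inputs from the documents.** Per-arm sizes 18 (glenohumeral), 25 (bursa), 25 (hip), 31 (biceps); two-sided 0.05; chi-squared test. **Assumed, because the documents are silent:** all side-effect rates, 15% loss, 20% of places filled by someone already counted in another cohort, and no continuity correction unless stated.

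**The plan's own figure.** There is none for side effects. The pain and function sizes cannot be reproduced, because no SD is given and the scale of the 10% and 25% differences is not defined. Solved backwards, (1.96 + 0.84) × √(2/n) gives standardised effects of 0.93, 0.79 and 0.71 at n = 18, 25 and 31. These say nothing about a difference in proportions.

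**Precision within a structure.** The half-width of the 95% interval for a risk difference with rate p in both arms is 1.96 × √(2p(1−p)/n). At p = 0.10:
- n = 18: 1.96 × √(0.18/18) = 0.196
- n = 25: 1.96 × √(0.18/25) = 0.166
- n = 31: 1.96 × √(0.18/31) = 0.149

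Only 1.8, 2.5 and 3.1 events per arm are expected at that rate, so this normal-theory width is a guide only. An exact check points the same way. With no events in an arm, the upper 95% limit for its rate, 1 − 0.025^(1/n), is 18.5%, 13.7% and 11.2%.

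**Power within a structure.** Exact enumeration of the uncorrected Pearson test:

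| Assumed rates | n = 18 | n = 25 | n = 31 |
|---|---|---|---|
| 5% v 15% | 13% | 21% | 27% |
| 10% v 20% | 12% | 17% | 20% |
| 10% v 30% | 32% | 45% | 52% |
| 20% v 40% | 26% | 35% | 41% |
| 10% v 40% | 56% | 73% | 81% |
| 10% v 50% | 79% | 91% | 96% |

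Only large differences are reliably detected. With Yates' correction, 10% v 30% falls to 17%, 27% and 39%.

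**Overall, stratified by structure.** The per-arm total is 18 + 25 + 25 + 31 = 99. This is a ceiling and one reading of the text: if the 50 participants cover bursa and hip together, it is 18 + 25 + 31 = 74. With 15% loss and 20% overlap, strata of 12, 17, 17 and 21 give 67. Half-widths at p = 0.10:
- 99: 1.96 × √(0.18/99) = 0.084
- 74: 1.96 × √(0.18/74) = 0.097
- 67: 1.96 × √(0.18/67) = 0.102

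Cochran-Mantel-Haenszel (CMH) power by simulation at 99 per arm is 68% (5% v 15%), 51% (10% v 20%), 95% (10% v 30%) and 88% (20% v 40%). At 67 per arm it is 50%, 37%, 85% and 73%.

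**Cost of combining.** If only the biceps cohort differs (5% v 20%, the others 5% v 5%), CMH power is 25%, against 47% for the biceps test alone.

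**The case against.** **Per-structure analysis answers the aim.** Aim b names the four structures, and section 8 analyses them separately. Sizing a trial on efficacy and leaving safety unpowered is common and is not in itself an error. This stands. A reader might infer that the plan is wrong not to pool, or that an overall test should replace the per-structure tests. The documents do not support that: it would change the question asked and would dilute an effect confined to one structure.

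**Four tests and false positives.** A reader might infer that running four tests seriously inflates the chance of a false rejection. That depends on a choice the plan does not state. At common rates of 5% to 30%, the chance that at least one of the four rejects is 7.6% to 19% with the uncorrected Pearson test, but 0.3% to 8.6% with Yates' correction and 0.5% to 9.1% with Fisher's test. The point here does not rest on it.

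**Within-structure testing is only implied.** This is true. If one test of all participants was meant, the precision problem within structures falls away. The missing estimate, interval, stratification and counting rule remain.

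**All rates are assumed.** Also true. Side effects are actively elicited, so rates could be low or high, and no single power figure describes this trial. For very large differences the planned tests are adequate or nearly so.

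**Conclusion.** The point holds as a gap in analysis and reporting. For one of its two aims the plan names a test and nothing else, and on the natural reading that test is applied in cohorts too small for non-significance to support the stated hypothesis. At an assumed 10% rate in both arms, differences of roughly 15 to 20 points would remain possible within a structure. A stratified overall estimate would narrow that to about 8 to 10 points, depending on whether 99, 74 or 67 per arm contribute.

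The conclusion rests on the separate-analysis statement covering side effects, on 50 participants each for bursa and hip, and on the assumed rates. If the 50 cover both structures together, those two cohorts are smaller and their intervals wider. The overall comparison is no cure for low power, since it too falls short of 80% for 5% v 15%. Its main value is the interval.

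**What to change.** Amend the SAP for aim b as follows.

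1. Keep the per-structure analyses. Beside each test, report the risk difference with a 95% confidence interval by an exact or score method, and state which form of chi-squared test is used.
2. Add, as a prespecified supplement, one overall comparison of participants with any side effect, stratified by structure: a CMH test with a stratified risk difference and 95% interval.
3. In that comparison count each participant once, by first structure and assigned arm. Use events before any second-structure injection as the main count, and all events to 6 months as a sensitivity analysis.
4. Tabulate side effects by type, arm and structure, so that the profile named in aim b stays visible when events are combined into any side effect.
5. State that conclusions are read from the intervals and that non-significance is not taken as similarity. No margin is given, so the intervals show only which differences are not excluded.

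The cost is SAP wording and a written counting rule; no new data or visits are needed. There are two downsides. The overall estimate assumes a broadly common effect and dilutes a single-structure one, so it is added to the per-structure results and does not replace them. Stopping the main count at a second-structure injection shortens observation for some participants, possibly unequally by arm, which is why the 6-month count is shown beside it.
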